14.3.11 QUALITY OF LIFE

All Quality of Life (QoL) analyses will be performed on the FAS. Scales from the EORTC-QLQ-C30 and items from the Brief Pain Inventory – Short Form, EORTC-QLQ-FA12 and Suppository Acceptance Questionnaire at each time point and changes from baseline will be summarized using descriptive statistics. Details of the scoring algorithms used to generate the QoL scores will be described in the SAP.

A Statistical Analysis Plan (SAP) will be developed and the analysis will be performed by a statistician using SAS {version TBD}.

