	
and resolves spontaneously or responds to conventional medical interventions.
 
2) Grade 4 non-hematologic (non-laboratory) toxicity of any duration
 
3) Grade 3 or Grade 4 febrile neutropenia of any duration not caused by doxorubicin. It is well known that a dose-dependent, reversible leukopenia and/or neutropenia are the predominant manifestations of doxorubicin hematologic toxicity and are the most common acute dose-limiting toxicities of this drug. With the recommended dose schedule, leukopenia is usually transient, reaching its nadir 10 to 14 days after treatment with recovery usually occurring by the 21st day.
 
4) Grade 3 thrombocytopenia in combination with a Grade 3 or greater blood and lymphatic system disorder, not attributable to doxorubicin
 
5) Grade 3 AST or ALT that is associated with a Grade 2 or greater rise in bilirubin
 
Growth factor support can be administered during combination cycles, except during Cycle 1 in the Dose Escalation Cohorts. The recommended Phase 2 dose (RP2D) may be defined as the highest dose administered at which no more than 1 patient (out of 6) experiences a DLT and the dosage form, including the dosing frequency, is acceptable to patients.
 
Cohort Expansion
 
After the Dose Escalation Part is completed, 16 patients will be enrolled into a Dose Expansion Cohort at the MTD of the combination of NOX66 and doxorubicin. All patients will enter directly into 21-day combination cycles and will be given NOX66 therapy for 7 days and doxorubicin will be administered on Day 2 (1 hour after the morning dose of NOX66 dose is administered). This will be followed by a 2-week rest period. Treatments will continue up to 6 cycles.
 
Treatment will be terminated upon disease progression, unacceptable toxicity or a maximum of 6 cycles. In patients who develop Grade 3 or 4 toxicity determined to be related to NOX66, the Investigator may reduce the dose or frequency of dosing by one level so that the patients can remain in the study. All patients will be actively followed up for about 14 months following completion of Cycle 6 (including scheduled visits every 3 months) followed by telephone follow-up / chart review, for progression free survival (PFS) and overall survival (OS), at 15 and 18 months following completion of Cycle 6.
 
Pharmacokinetics
 
During the Monotherapy phase, on Day 1 blood samples will be collected for PK analysis of idronoxil at pre-dose (within 15 minutes prior to dosing) and at 1, 2, 3, 4, 6, and 8 hours post application. On Day 2, a pre-dose sample will be collected prior to application of NOX66. This sample can be collected in the clinic or at the patient's home. Exact times for dosing and blood sampling will be recorded. If a bowel movement occurs, during the collection period, the time of each bowel movement should be recorded, and the collections should continue as planned. Blood plasma will be analysed for the quantification of

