8.1.1 DOSE-ESCALATION

For all dose escalation cohorts, there will be 7 days of monotherapy treatment with NOX66 followed by a 5- day washout period prior to the start of combination cycles of NOX66 and doxorubicin. The purpose of the monotherapy treatment is to evaluate the safety and tolerability of NOX66 when administered alone and as well as single and multiple dose PK of idronoxil.

The dose-escalation part of the study will include three planned Treatment Groups (800, 1200, 1800 mg daily) of 3 patients each. The first 3 patients will be entered at Dose Level 1 and will receive daily doses of NOX66 for 7 days. All of these doses, except for the 1800 mg have been evaluated in 2 previous clinical trials and have been relatively well tolerated as monotherapy for 14 days and in combination with carboplatin for 42 days.

After a rest period of 5 days and if no significant toxicities (DLT equivalent toxicity) have occurred, patients will enter the combination therapy part of the study which will consist of up to 6 x 21-day treatment cycles. Each cycle will consist of 7 days of NOX66 (at the assigned dose), doxorubicin (75 mg/m²) on Day 2 of the 21-day cycle (administered at approximately 1 hour after rectal application of NOX66) and a rest period of 2 weeks.

For the 800 mg and 1200 mg dose levels NOX66 will be administered twice-daily (BID) with a 400 mg or 600 mg suppository, respectively, and the 1800 mg dose level will entail administration of a 600 mg suppository three times daily (TID). In all cohorts, doxorubicin will be given initially at 75 mg/m² as an intravenous infusion over 15 minutes (or as per standard of care). This dose may be reduced to 60 mg/m², at the Investigator's discretion for unacceptable Grade ≥ 2 toxicity. A dose reduction of 50% is recommended if serum bilirubin is 1.2 -3.0 mg/dL prior to a cycle. If serum bilirubin is 3.1-5.0 mg/dL prior to a cycle, a 75% dose reduction of doxorubicin is recommended.

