8.3.6 PATIENT REPLACEMENT

The following guidelines will be used to determine when a patient can be replaced

- During the Monotherapy period in the Dose Escalation part of the study, if a patient who is not tolerating the assigned dose of NOX66, may be replaced with another patient, following a joint decision between the Investigator and Medical Monitor. A maximum of 3 replacements is allowed in each dose level in the Monotherapy period.
- If any patient withdraws consent during Monotherapy period or during Cycle 1, he/she will be replaced with another patient.
- If any patient who has not taken at least 80% of the prescribed daily doses of NOX66 during Monotherapy period and Cycle 1, will be replaced with another patient.
- During the Dose Expansion Part, patients who have not completed at least 2 complete cycles of treatment, will be replaced with additional patients, until at least 12 patients have completed 2 cycles.

The recommended phase 2 dose (RP2D) may be defined as the highest dose of the combination administered if no DLTs are observed and the dosage form is acceptable to patients.

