10.2 INVESTIGATIONAL PRODUCT ADMINISTRATION

10.2.1 ADMINISTRATION

Depending on the cohort/dose level, 2 to 3 suppositories will be self-administered daily for 7 days in the Monotherapy period (only for Dose Escalation part) and/or in combination with doxorubicin for the treatment cycles. In this study, the dosage forms will be inserted rectally either twice (12 hours apart) or three times (8 hours apart) per day. In patients who have regular bowel movements (i.e. within several hours after awakening) patients will be instructed to insert the suppository after the bowel movement. To promote regular movements, patients should be encouraged to consume a high fiber diet, with adequate amounts of water. In those patients who are not on a regular bowel movement schedule, insertion of the suppository should occur at regularly scheduled times individualized for the patient. If defecation occurs after NOX66 administration, no re-dosing is required. The next dose should be administered at the scheduled time. During the NOX66 and doxorubicin combination treatment cycles, if diarrhea occurs, the Investigator must follow standard management practices to manage the diarrhea to allow for NOX66 administration.

If any patients have difficulty with administering suppositories three times per day (8 hours apart) due to any personal reasons, dosing schedule can be changed to two times daily (3 suppositories per day) after Cycle 2. In this instance, patients can administer one 600-mg suppository in the morning and two 600-mg suppositories in the evening. While two suppositories are administered, each suppository needs to be inserted at least 5 minutes apart.

The dosing time for each suppository must be recorded by the patient in a diary which must be brought to the clinic at each visit. The dose escalation scheme is presented in [Table 1](#)

Proposed Starting Dose and Dose Escalation Scheme for NOX66

Table 1 Proposed Starting Dose and Dose Escalation Scheme for NOX66

Cohort	1	2	3
Increment	NA	50%	50%
Total daily dose (mg)	800	1200	1800
Daily regimen (mg)	400 BID	600 BID	600 TID

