11.6.2.2 Days 7 and 8 (± 1 day) Only for Dose Escalation

- On Day 7, assess and review TEAEs (Section [16](#)).
- On Day 7, collect urine and fasting blood samples for clinical laboratory tests ([Table 3](#)).
- On Day 7, perform a physical examination (including weight; Section [11.4.2.2](#)).
- On Day 7, administer questionnaires BPI-SF, EORTC QLQ-FA12 and Suppository Acceptance Questionnaire (SAQ).
- On Day 7, review treatment log (diary) and assess dosing compliance.
- On Day 7, review and record concomitant medications (Section [10.4](#)).
- On Day 7, collect blood samples for BNP, troponin 1, chemokines, cytokines and immunoassays prior to NOX66 administration.
- On Day 7, measure vital signs (blood pressure, pulse [radial or brachial (to be measured over 30 seconds if performed manually)], respiration rate and body temperature [oral or aural]; Section [11.4.2.1](#)) prior to NOX66 administration.
- On Day 7, administer the morning dose of NOX66 in the clinic.
- On Day 7, 12-lead ECGs will be performed in triplicate at -0.75, -0.5 and -0.25 hours prior to and at 1, 2, 5, and 8 hours post morning dose of NOX66. Holter monitoring will run from 8 to 24 hours post morning dose of NOX66.
- On Day 7, PK blood sampling pre dose and at 1, 2, 3, 4, 6, and 8 hours post application.
- On Day 8, PK blood sampling at 8 or 12 hours after the last dose of NOX66 on Day 7 for those on a TID or BID regimen, respectively. These samples may be obtained by a visiting healthcare professional at home or in the clinic.

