14.3 STATISTICAL METHODOLOGY

14.3.1 GENERAL STATISTICS METHODS

All data will be summarized by idronoxil dose group. For safety analyses, a summary group consisting of all dose groups combined may also be presented.

For all measurements, the baseline value will be the last measurement taken before the first dose of study drug, whether idronoxil or of idronoxil + doxorubicin depending on the cohort.

Standard summary statistics will be presented for all measurements. For continuous variables, the standard summary statistics will be the number of observations (n), mean, standard deviation, median, minimum and maximum. For categorical variables, the standard summary statistics will be the number and percentage of observations in each category. Categories that are specified on the eCRF which contain no observations will be presented in the data summaries with a value of 0.

An AE with a completely missing start date will be assumed to start one minute after the date-time of the first idronoxil dose. If the severity of a reported AE is missing, it will be assumed that the event is severe; similarly, if the relationship of a reported AE to study treatment is missing, it will be assumed that the event is definitely related to treatment. No other missing data will be imputed. Incomplete start dates for Adverse Events and Concomitant Medications and incomplete end dates for AEs will have missing parts imputed by a conservative procedure which will be specified in the Statistical Analysis Plan (SAP).

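### The planned change from baseline for the Suppository Acceptance Questionnaire cannot be computed as defined, and from Cycle 4 Day 1 the 1800 mg summaries may mix three-times-daily with twice-daily dosing

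*Combined protocol and SAP*

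**What the plan says.** **Role of acceptability.** The synopsis says the recommended Phase 2 dose (RP2D) may be defined as the highest dose with at most 1 of 6 patients having a dose-limiting toxicity (DLT), provided that "the dosage form, including the dosing frequency, is acceptable to patients". Section 8.3.6 words it differently: the highest dose given "if no DLTs are observed and the dosage form is acceptable to patients". It does not mention dosing frequency.

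**Regimen and switch.** Section 8.1.1 and Table 1 make 1800 mg the only TID level (one 600 mg suppository per dose). Section 10.2.1 provides that, for patients who have difficulty with TID, the "dosing schedule can be changed to two times daily (3 suppositories per day) after Cycle 2". They then use one 600 mg suppository in the morning and two in the evening, so the daily total is still 1800 mg.

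**Analysis.** Section 14.3.1: "All data will be summarized by idronoxil dose group". The same section takes as baseline the last measurement before the first study drug dose. Section 14.3.11 says of the SAQ, among other instruments: "Suppository Acceptance Questionnaire at each time point and changes from baseline will be summarized using descriptive statistics".

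**Collection.** In escalation the first SAQ is on Monotherapy Day 7 (Section 11.6.2.2). In expansion it is on Cycle 2 Day 1 (Section 11.6.2.5). The SAQ is not listed at Screening, Monotherapy Day 1 or Cycle 1 Day 1, in the text or in Table 4. Section 11.4.4, however, places it on Day 1 of every combination cycle, which read literally includes Cycle 1.

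**The concern.** There are two separate defects.

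First, a change from baseline is planned for an instrument with no scheduled pre-dose value. If a programmer substitutes the first on-drug score, the result is drift during treatment, not a change from baseline.

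Second, the patients most likely to leave TID are those who find it hard. After switching they stay in the 1800 mg group and rate a different schedule under the same heading. No summary clearly captures the switch, although it is the most direct evidence that TID was not acceptable to that patient. If 1800 mg becomes the maximum tolerated dose (MTD), TID is the frequency to be judged for the RP2D, and later scores could rise only because patients changed schedule.

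The Cycle 3 and 5 troughs in Section 14.3.9 have the same grouping problem. A switched patient's last dose of the day is larger and the interval longer than for a patient still on TID.

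**Working it through.** The documents give no rate, threshold or sample size for acceptability, so there is no planned figure to reproduce.

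**Step 1. Is there a baseline?** Questionnaires scheduled at each visit that could supply a pre-dose value:

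| Visit | SAQ listed? |
|---|---|
| Screening (11.6.1) | No |
| Monotherapy Day 1, escalation (11.6.2.1) | No |
| Cycle 1 Day 1, first dosing day in expansion (11.6.2.4) | No |

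Under the visit lists and Table 4, the number of patients with a scheduled pre-dose SAQ is 0. Section 11.4.4 read literally adds Cycle 1 Day 1. In escalation that visit follows seven days of NOX66, so it is not a baseline. In expansion it could be completed before the first dose, but the patient would be rating a suppository not yet used in treatment.

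**Step 2. Which SAQ time points can contain switched patients?** The switch is allowed after Cycle 2. The Cycle 3 Day 1 form is taken to be completed before Cycle 3 dosing, which matches the order of procedures in Section 11.6.2.6, so it still reflects TID use.

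- Escalation, 7 time points: Monotherapy Day 7, C2D1, C3D1 | C4D1, C5D1, C6D1, C6D21 or early termination. Those after the bar, 4 of 7, can be mixed.
- Expansion, 6 time points: C2D1, C3D1 | C4D1, C5D1, C6D1, C6D21 or early termination. Here 4 of 6 can be mixed.

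**Step 3. How large could the effect be?** All rates here are assumptions. Let u be the share who find TID unacceptable, s the share of those who switch, and q the share of switchers who then rate the form acceptable. Assume that only dissatisfied patients switch and that nobody drops out.

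- True acceptance of TID = 1 − u
- Acceptance shown at 1800 mg from C4D1 = (1 − u) + u·s·q
- Overstatement = u·s·q

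| u | s | q | True | Shown | Overstatement (points) |
|---|---|---|---|---|---|
| 10% | 100% | 100% | 90% | 100% | 10 |
| 30% | 0% | any | 70% | 70% | 0 |
| 30% | 50% | 50% | 70% | 0.70 + 0.30 × 0.25 = 77.5% | 7.5 |
| 30% | 100% | 100% | 70% | 100% | 30 |
| 50% | 100% | 100% | 50% | 100% | 50 |

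Across u = 10% to 50%, the minimum is 0 and the maximum equals u. The model cannot give a negative value, because of how it is built. Before C4D1 the overstatement is zero.

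**Step 4. Would showing only patients still on TID solve it?** No. Acceptance among them is (1 − u)/(1 − u·s). With u = 30%, this gives 0.70/0.85 = 82.4% at s = 50% and 0.70/0.70 = 100% at s = 100%, against a true 70%. The switch count must be reported alongside.

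**Step 5. Troughs.** Section 10.2.1 spaces TID doses 8 hours apart and twice-daily doses 12 hours apart. On TID the last dose of the day is 600 mg; after a switch it is 2 × 600 = 1200 mg. The Day 7 pre-dose and Day 8 samples in Cycles 3 and 5 can therefore follow different doses and intervals within one dose group. The documents give no concentrations, so the effect cannot be sized.

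**The case against.** The strongest reply is that the plan already gives a clean reading of TID. The SAQ is summarised at each time point, and Monotherapy Day 7, C2D1 and C3D1 all precede any permitted switch. That stands. A reader might infer that TID will look more acceptable than it is; the documents support only that it may, from C4D1 onward.

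A reader might also infer that the missing baseline favours TID. It does not: a change score with no baseline gives no number and so no bias. Nor can one say flatly that no baseline will be collected, because Section 11.4.4 conflicts with the visit lists.

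The link to the RP2D is loose. Both definitions say only what the RP2D may be, neither names an SAQ visit or threshold, and Section 8.3.6 omits frequency. Acceptability is an exploratory objective, and the Safety Review Committee meets after each cohort's Cycle 1, before any switch in that cohort. All this limits the consequence, but acceptability remains a stated RP2D condition.

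Section 11.1.2.3 does not list the SAQ among the instruments expressed as change from baseline, so the phrase in Section 14.3.11 may be loose list wording. That is plausible, and a reason to correct the phrase. Section 14.3.3 counts changes in idronoxil dose, which might catch the larger evening dose, but with the daily total unchanged the text is ambiguous.

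Finally, Section 14.3.12 leaves further detail to a later statistical analysis plan (SAP). That is the right place for the correction, but a general deferral does not undo the grouping and change score already written.

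**Conclusion.** The point holds in limited form. The SAQ change from baseline cannot be computed as defined under the visit lists and Table 4. Independently, 1800 mg SAQ scores from C4D1 onward and the Cycle 3 and 5 troughs may mix two regimens, and no planned summary clearly captures the switch.

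The overstatement of TID acceptance is of unknown size. A rise from 70% to 100% might be inferred as the expected effect, but it is a ceiling: it needs 30% to find TID unacceptable, all of them to switch, and all switchers to be satisfied. None of these rates is in the documents, and nothing shows that patients would rate two evening suppositories better. The issue arises only if 1800 mg is reached. An effect on the RP2D is possible, not shown, because the documents do not say which SAQ visits inform it. The correction is still worth making, because it is cheap and concerns a stated RP2D condition.

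**What to change.** 1. In Section 14.3.11, drop the change from baseline for the SAQ.
2. Summarise 1800 mg SAQ scores, and the Cycle 3 and 5 troughs in Section 14.3.9, by the regimen actually used in the relevant cycle. For a Day 1 SAQ this is the cycle just completed.
3. Report the number and timing of switches from TID to twice daily as n/N, with N being all patients who started TID. Count each switch as non-acceptance of TID.
4. State that the RP2D acceptability reading for TID rests on the pre-switch time points (Monotherapy Day 7 in escalation; C2D1 and C3D1 in both parts) together with the switch count, not on scores from remaining TID patients alone.
5. Reconcile Section 11.4.4 with Section 11.6.2.4 and Table 4 on the Cycle 1 Day 1 SAQ, and the synopsis with Section 8.3.6 on the RP2D definition.

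The cost is wording in the protocol and in the SAP due before the expansion cohort opens. Section 10.2.1 already requires a diary of dosing times, so no new data are needed and patient management does not change. The downside is that reported acceptability of TID may be lower.

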14.3.12 STATISTICAL ANALYSIS PLAN

Further details on statistical methods, presentations, and rules for data handling will be provided in a Statistical Analysis Plan that shall be approved prior to the opening of the Dose Expansion Cohort.

14.4 INTERIM AND ADDITIONAL ANALYSIS

An interim analysis will be performed after all patients in the Dose Escalation cohorts have either discontinued or completed 3 treatment cycles, whichever comes first. A second interim analysis may also be performed after 50% of the patients in the Dose Expansion Cohort have either discontinued or completed 3 treatment cycles.

The results from these analyses will not be used to modify the study design or to stop the study.

15 MONITORING**15.1 MONITORING OF CASE REPORT FORMS**

The study will be monitored by a CRO on behalf of the Sponsor. Monitoring will be conducted according to ICH GCP guidelines and Monitoring CRO SOPs. An initiation meeting will be conducted by CRO. At this meeting the protocol, the procedure for completing the eCRFs, and pertinent aspects of the eCRFs will be reviewed with the Investigator and all study staff.

The Monitor will visit the Investigator at regular intervals to review the progress and conduct of the study. The CRFs will be checked for completeness and accuracy against the patient records, patient charts, laboratory reports, X-ray reports and scans as specified in the monitoring plan. Anonymity of the patient will be maintained at all times.

Regulatory authorities, the IRB or the Sponsor may request access to patient clinical notes and other relevant study documentation for an on-site audit or inspection. The Investigator is obliged to facilitate this process by allowing full access.

15.2 SAFETY DATA MONITORING

The Medical Monitor will review and evaluate all toxicities causally associated with NOX66 alone in combination with doxorubicin in each cohort.

15.2.1 SAFETY MONITORING AND OVERSIGHT

After each cohort has completed Cycle 1, the SRC meeting will be held. The meetings will be comprised of the enrolling Investigators, a representative from the Sponsor, and may also include a cardiologist or other outside consultants at the Sponsor's discretion. The role is to assess any DLTs and adjudicate the MTD and whether the study should continue or be terminated based on efficacy, safety and tolerability data. A charter for the SRC will be developed prior to initiation of the clinical study.

If available, PK, PD, and efficacy data will also be included for review at the SRC meeting

15.2.1.1 AE Reporting

All AEs are graded according to NCI-CTCAE v5.0. AEs are captured from the time of consent and must be reported in the eCRF.

. Some events may make the patient ineligible for enrollment. Unanticipated events should be reported to the IRB, according to its requirements. Patients will be questioned at every visit after the first dose until the last follow-up visit regarding the occurrence and nature of any TEAEs. All TEAEs will be reported, whether or not they are deemed to be related to investigational product.

A description of the event or diagnosis including dates, severity, relationship to the investigational product, action taken and outcome, and whether or not the event was also serious, must be reported on the AE eCRF for each TEAE recorded in the patient's chart.

